4 STUDY DESIGN

4.1 Study design schema

[figure not shown]

Figure 4a Summary of Study Schema.

See Table 5a for details of schedule of assessments and data collection at each assessment.

4.2 Overall design

This is a prospective observational study involving infants born preterm who require care in a participating Victorian Level 6 NICU. The overall purpose is to generate a large dataset to robustly define the different early life preterm respiratory phenotypes, and then interrogate that dataset to determine the relationship between these phenotypes (and biomarkers used to define them) and later BPD and 1- and 2-year respiratory health status.

Infants born between 22+0 and 31+6 weeks' gestation who meet all inclusion (and no exclusion) criteria and provide prospective written informed parental/guardian consent will be included in this study. This gestational age (GA) range has been chosen to align with those included in the Australian and New Zealand Neonatal Network (ANZNN) database. The ANZNN database aims to capture all preterm infants born in Australia and New Zealand (opt out consent).

The BLUEPRINT study expects to enrol 550 infants over the course of the 3-year enrolment period across 5 tertiary level NICUs in Victoria.

Longitudinal observations and measurements will be taken from plasma proteins, LUS and EIT, in addition to a standardised set of clinical measured designed to reflect physiological status, delivered clinical care and known antenatal, maternal and postnatal respiratory outcome risk factors. All participating infants will receive standard NICU care as per the treating institution.

Eligible infants will be consented prospectively, and eligibility confirmed prior to study enrolment. Prior to blood sampling and lung imaging, the parents and/or legal representative of the infant will be reminded of their participation in the BLUEPRINT study. Prior to discharge, patient contact details will be confirmed by the study team for follow-up study timepoints. Post-discharge follow-up at 1 and 2 years of corrected gestational age is not mandatory but encouraged. Follow-up assessments will be completed at the MCRI ([name]).

4.3 Study population

4.3.1 Eligibility Criteria

Infants born between 22+0 and 31+6 weeks' gestation admitted to a participating centre who meet all the inclusion criteria and none of the exclusion criteria are eligible for enrolment on the BLUEPRINT study.

4.3.2 Inclusion Criteria

Each infant must meet all inclusion criteria to be eligible for enrolment on this study:

1. Born between 22+0 and 31+6 weeks' gestation.
2. Birth admission in a participating perinatal Victorian NICU.
3. The infant has a parent/legal representative capable of understanding the informed consent document and providing consent on the infant's behalf AND consent is obtained antenatally or within 72 hours from birth.

4.3.3 Exclusion Criteria

If any of the following exclusion criteria are met, the infant will be ineligible for enrolment on this study:

1. Infants with a known major congenital anomaly (such as oesophageal atresia and central nervous system anomalies), congenital cardiac disease, congenital diaphragmatic hernia, congenital lung abnormalities and/or pulmonary hypoplasia.
2. Pulmonary hypoplasia due to anhydramnios **or** oligohydramnios before 22 weeks in which the neonatal clinician anticipates that pulmonary hypoplasia related respiratory failure will be the major respiratory problem in early postnatal life.
3. Primary cause of admission unrelated to prematurity.
4. Refusal of informed consent by their legally acceptable representative.
5. The infant does not have a parent/legal representative who can provide informed consent or consent cannot be obtained before 72 hours of age.

In addition, any infant identified by the treating medical team may be excluded from the study at the request of the treating clinician in consultation with the site lead investigator.

4.4 Recruitment of potential infants

4.4.1 Recruitment planning

Any infant born into a participating perinatal Victorian NICU between 22+0 and 31+6 weeks' gestation will be eligible to participate in the BLUEPRINT study if they meet all the inclusion and none of the exclusion criteria (as described in section 4.3.1). The study design is an observational longitudinal prospective study for which prospective consent will be obtained for all enrolled infants. Eligible infants will be screened as per section 4.5.2.

Infants will be asked to attend a follow-up respiratory and development assessment at 1 and 2 years of corrected age. All follow-up assessments will be conducted at the MCRI. Whilst follow-up assessments are not mandatory, they are strongly encouraged. The MCRI BLUEPRINT study team will contact the family prior to their scheduled follow-up assessment timepoint as a reminder of their participation in the BLUEPRINT study. Birthday cards will be sent by the study team on behalf of the BLUEPRINT study on the infant's first and second birthdays.

4.4.2 Stages of recruitment

Screening: Potentially eligible infants will be identified from admission from the participating NICUs, antenatal and inpatient ward lists by the site study investigators and research nurses at each site.

Screening Log: A record of all eligible infants will be maintained in a dedicated REDCap screening database and updated by a member of the study team.

Enrolment: Once a potentially eligible infant (antenatally or postnatally [before 72 hours of age]) has been identified, a member of the study team will first determine a suitable time to meet with the parent(s)/legal guardian. This will be done in consultation with the treating clinical staff to ensure the psychological circumstances and stressors of the parent/legal guardian, as well as the clinical events and situation, are considered.

At a suitable time, a member of the study team will meet with the parent(s)/legal guardian in the antenatal wards or NICU (or via telephone or digital communications platforms if access restrictions are in place) to obtain consent (see Section 4.5). If informed consent has been provided and the infant still meets eligibility criteria at birth, the infant will be enrolled into the study and allocated a unique study code.

If the mother carries beyond 31+6 weeks' gestation, or consent is given after 72 hours from the infant's birth, the infant will no longer be eligible for enrolment and any signed consent form will be void. The signed consent form will be maintained by the site staff and archived as per the study protocol.

Concurrent Research Enrolment: The BLUEPRINT study encourages and supports concurrent enrolment with other clinical research studies unless the co-enrolment compromises the integrity of BLUEPRINT outcomes. Concurrent study enrolment will enhance recruitment efforts at participating sites, and potentially allow streamlining of data collection to reduce participant burden. Any patient who is identified as eligible for enrolment on multiple research studies, should be discussed and enrolled at the discretion of the Site Principal Investigator. Should further discussion be required, the Co-ordinating Principal Investigator should be contacted prior to enrolling the infant on BLUEPRINT. Enrolment of BLUEPRINT participants on other research studies or clinical trials should be documented in the participant's medical record and in REDCap.

The policy on Concurrent Research Enrolment is as follows:

1. All trials and studies that likely involve participants who are also eligible for the BLUEPRINT study must be discussed with the Principal Investigator and Co-ordinating Principal Investigator, and the protocols shared with the study team, prior to co-enrolling any infants.
2. All such studies may or may not be compatible with the BLUEPRINT study, and a full discussion will be undertaken with all parties to resolve potential for co-enrolment.
3. Enrolment of BLUEPRINT participants in concurrent studies that involve consent for the child and family must be documented within the participant's medical record and on the Final NICU CRF within the BLUEPRINT REDCap Data Management System (DMS).

4.5 Consent

The investigator or delegated member of the study team will discuss the study with the infant's parent/legal guardian either in the antenatal period or within the first 72 hours after birth. The investigator will provide the Participant Information and Consent Form (PICF) to the parent/legal guardian. This document will describe the purpose of the study, the procedures to be followed, biospecimen sample collection requirements and the risks and benefits of participation.

The investigator will check that the parent/legal guardian comprehends the information provided and answer any questions about the study. The parent/legal guardian will be invited to provide written consent. Consent will be voluntary and free from coercion.

The investigator who conducted the consent discussion will also sign the informed consent form and it will be documented in the infant's medical record that consent has been provided. When all the inclusion/exclusion criteria have been addressed and the eligibility of the infant confirmed, the infant is considered enrolled. The signed consent form will be filed in the infant's shadow folder maintained at each participating site. A copy of the consent form will also be given to the parent/legal guardian.

Written consent will be primarily sought. If the parent/legal guardian is unable to be approached in person, verbal consent will be sought over the telephone or via teleconference. Digital recording of tele-consent will not occur. However, documentation of the parent/legal guardian's contact details, outcome of verbal consent and follow up will be documented in the "Record of Verbal or Virtual Consent" form within the study's REDCap (Research Electronic Data Capture) screening log. If verbal or virtual consent is obtained, the investigators will follow up with the parent/legal guardian for written consent at the next available opportunity. Having a newly-born preterm baby in the NICU is stressful. The timing for follow up of written consent will be coordinated with the treating clinical team to ensure minimal distress or inconvenience for the parents/guardians.

Regular contact, in the form of yearly newsletters and birthday cards, will be made with the families leading up to the 2-year assessment.

Documentation in the patient's medical record will be made for any consent (verbal, virtual or written) related to this study as per institutional standard practice.

5. STUDY SCHEDULE OF ASSESSMENTS

5.1 Study timeline

The study will be conducted over a 5-year period from the date the first infant is enrolled. Screening and prospective eligibility will be assessed antenatally by a delegated member of the study team. Prospective consent will be obtained by the infant's parent/legal guardian and can be obtained up until 72 hours of life (prior to plasma sampling). Eligibility will be confirmed prior to enrolment and documented as per the manual of operating procedures. Infants enrolled in the study will undergo assessments as outlined in the Schedule of Assessments (section 5.2) and summarised in Table 5a. Follow-up assessments will occur at 1 and 2 years corrected gestational age. Infants will participate no longer than 3 months after they turn 2 years of corrected age. In addition, relevant maternal/perinatal data, and adverse events (AEs) and other safety events/risks will be collected, based on maternal interviews, extracted from medical charts, and entered in the study REDCap database.

5.2 Schedule of assessments

Table 5a Study Timeline and Schedule of Assessments

Schedule of Primary Assessments											Follow-up Assessments	
Assessment/ Procedure	Screening	Baseline (Birth)	24h post- birth	48h post- birth	72h (±12h) post- birth	Day 7 (±12h)	Day 14 (±1d)	Day 28 (±1d)	36wks PMA (+7d)	End of NICU Stay	Year 1 (corrected age)	Year 2 (corrected age)
Informed Consent and Documentation of Eligibility	X [#]											
Maternal data collection [^]		X										
Neonatal and Respiratory data collection [^]		X	X	X	X	X	X	X	X	X		
Lung Function Assessment (LUS and EIT)			(X)	(X)	X	X	X	X	X		X	X
Proteomic profiling (Plasma Sampling)					X	X						
BPD Assessment*									X			
Clinical Health Assessment											X ¹	X ¹
Respiratory Follow-up (Questionnaire)											(X)	(X)
Development Assessment (PARCA-R)											(X)	(X)
Adverse Event Reporting			X	X	X	X	X	X	X			

(X) denotes optional assessments

[#] Consent is permitted to be obtained up until 72 hours of life, prior to plasma sampling

[^] Clinical data and Perinatal Medical History will be collected from Patient Medical Records

*BPD Diagnosis and Severity assessed according to the Walsh and Jensen criteria

¹ Clinical Health Assessment to be performed if patient returns in-person for FU timepoints

Study Name: The BLUEPRINT Study

Protocol Number: 107608

Version & date: Version 1.2, dated 9 July 2024

6. STUDY VISITS AND PROCEDURES

6.1 Description of procedures

Eligible infants for whom consent have been obtained will be studied. Prior to lung imaging or plasma sampling measurement at 72 hours and 7 days after birth, a member of the study team will approach the clinical team (medical or nursing staff) to re-confirm suitability to participate in the study. This will be repeated prior to lung imaging measures at Days 14, 28 and time of BPD diagnosis.

The parent/legal guardian will be contacted by a member of the study team prior to assessment at Days 14, 28 and time of BPD diagnosis, and again for the 1 and 2 year follow-up assessments to ensure that they are still aware of their infant's participation in the BLUEPRINT study and provide an opportunity to ask any questions or withdraw from the study, as per the manual of operating procedures.

6.2 Notes on study visits

6.2.1 Screening

Screening data will ascertain whether an infant is eligible for the study, the process of consent and outcome will be documented in the infant's medical record. Screening will occur prior to an infant's birth or up to 72 hours after birth as detailed in Section 4.4 – *Recruitment of Potential Infants*. Each site will maintain a screening log of all screened mothers and infants, indicating who is eligible and who is not, and of eligible mothers who have consented to the study and who have refused study participation and why (if known).

Screening information (i.e. the Screening Log) will be recorded and maintained directly within a BLUEPRINT REDCap Data Management System (DMS). Note: this Screening Database is maintained separate to the main BLUEPRINT study database. Refer to the BLUEPRINT CRF Completion Guidelines for further information regarding data entry.

The following **Eligibility Data** will be documented within the infant's medical record, prior to transcription into BLUEPRINT REDCap database:

- Confirmation that the infant meets the eligibility criteria for the study (i.e. all inclusion and no exclusion criteria)
- Documentation of Participant Identification Number (PID) assigned.

6.2.2 Standard study visits

Screening

 • Documentation of Consent and Eligibility status
Baseline (Birth)

 • Maternal Data Collection • Neonatal and Respiratory Data Collection
24h and 48h post-birth

 • Neonatal and Respiratory Data Collection • Lung function assessment (LUS and EIT) (optional)
72h post-birth

 • Neonatal and Respiratory Data Collection • Lung function assessment (LUS and EIT) ± 12h • Plasma Collection (proteomic profiling)
Day 7

 • Neonatal and Respiratory Data Collection • Lung function assessment (LUS and EIT) ± 12h • Plasma Collection (proteomic profiling)
Day 14 and Day 28

 • Neonatal and Respiratory Data Collection • Lung function assessment (LUS and EIT) ± 24h
36 weeks' PMA

 • Neonatal and Respiratory Data Collection • BPD Assessment (Walsh, Jensen criteria)
End of NICU

 • Neonatal and Respiratory Data Collection
Follow-Up; Year 1 and Year 2

 • Respiratory Follow-up • Lung function assessment (LUS and EIT) • Developmental Follow-up (PARCA-R)

6.2.3 Clinical Data

The following data will be collected by a member of the study team from the participating infant's and their mother's medical files/records, investigative reports, and bedside monitors:

Antepartum Data: These data will be completed, and entered directly into the BLUEPRINT REDCap DMS at a suitable time following infant enrolment, including:

- Documentation of mode of consent
- Confirmation that the infant meets the eligibility criteria for the study (i.e., all of the inclusion and none of the exclusion criteria)
- Documentation of Participant Identification Number (PID#)
- Maternal medical history
- Medication history
- Demographic information of the mother and infant, including:
 - Mother's year of birth
 - Mother's race/ethnicity (if consented to provide)
 - Infant's full date of birth, time of birth, sex
- Pregnancy data, including:
 - Gestational age (in weeks/days)
 - Birth weight (g)
 - Plurality of the pregnancy
 - Mode of delivery and reason
 - Fetal Growth Restriction
 - Reason for preterm birth
 - Documentation of the use of any antenatal steroids, or other emergency antenatal/perinatal medication
 - Documentation of any adverse events and/or safety issues

Delivery Room and initial NICU Stabilisation: A delegated member of the study team will enter the following data directly into the BLUEPRINT REDCap DMS at a suitable time following infant enrolment, including:

- Time of delivery/birth
- Use of delayed cord clamping and timing
- Delivered positive end-expiratory pressure settings/level; highest and lowest and duration
- Positive Inflating Pressure levels (if used)
- Fraction of inspired oxygen (FiO₂) delivered; lowest and highest levels and duration
- Duration of delivery room stabilisation
- Intubation status
- Heart Rate (HR); lowest reading
- Oxygen Saturation (SpO₂); lowest and highest levels
- Highest modified oxygenation index (SpO₂/ FiO₂) (calculated post hoc)
- Documentation of other delivery room interventions and/or medications used
- Final respiratory settings on departure from delivery room

First week of NICU care after birth: A delegated member of the study team will enter data directly into the BLUEPRINT REDCap DMS relating to the clinical course during the first 24, 48, 72 hours and at 7 days of life, including:

- Use of supplemental oxygen, including highest level of FiO₂ in the first 24, 48, 72 hours and 7 days of life
- Details of respiratory support including type of support and duration (including none, low flow and high flow nasal cannula, continuous positive applied pressure and other forms of non-invasive and invasive ventilation modalities)
- Highest pressure, flow, delivered volume settings as appropriate for all types of respiratory support used during the first 24, 48, 72 hours and 7 days of life
- Intubation and extubation events up to Day 7
- Survival status/date of death (during hospital stay, if applicable) / reason for death
- Documentation of any adverse events and/or safety issues
- Relevant respiratory and other treatments or outcomes, including:
 - Use of postnatal steroids, including types, timing and accumulated doses
 - Use, type, delivery method and dose of exogenous surfactant
 - Use of caffeine or other respiratory stimulants
 - Use of inotropes, including type and accumulated dose
 - Need for fluid or blood product bolus therapy
 - Haematological and biochemical investigation results
 - Use of antibiotics and proven culture positive results
 - Incidences of significant brain injury (IVH, periventricular leukomalacia), pneumothorax and pulmonary interstitial emphysema
 - Patent ductus arteriosus (PDA) and any associated treatment
 - Incidences of other clinical events or diagnoses that may impact respiratory status
- Details of blood sample collection
- LUS data including quality and number of images and LUS score
- EIT data including quality and number of images, belt size used and regional ventilation measures (centre of ventilation, %Tidal volume per region and inhomogeneity index)

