6.2.6 Day 14 and Day 28 Assessment

Previous studies of LUS to predict BPD status have suggested that Day 14 and Day 28 are the most useful time points.⁽²¹⁾ LUS and EIT images will be conducted on Day 14 and Day 28 after birth (with a \pm 24-hour window) as per 72 hours and Day 7 methods (see Section 6.2.4). Suitability to obtain imaging data and best timing will be re-affirmed with the clinical team. Where feasible, the parent/legal guardian will be notified of upcoming assessments as per the manual of operating procedures. In addition, the following clinical data will be collected:

- Type of respiratory support and use of supplemental oxygen at midday on Day 14 and Day 28
- All types and duration of respiratory support used between Days 8-14 and Days 15-28
- Intubation and extubation events since Day 7
- Survival status/date of death (during hospital stay, if applicable) / reason for death
- Documentation of any adverse events and/or safety issues
- Relevant respiratory and other treatments or outcomes, including:
 - Use of postnatal steroids, including types, timing and accumulated doses
 - Use, type, delivery method and dose of exogenous surfactant
 - Use of caffeine or other respiratory stimulants
 - Use of inotropes, including types, timing and accumulated doses
 - Use of pulmonary hypertensive treatments, including types, timing and accumulated doses
 - Use of antibiotics and proven culture positive results
 - Incidences of significant brain injury (IVH, periventricular leukomalacia), pneumothorax and pulmonary interstitial emphysema, necrotising enterocolitis and retinopathy of prematurity
 - Patent ductus arteriosus (PDA) and any associated treatment
 - Incidences of other clinical events or diagnoses that may impact respiratory status
- LUS data including quality and number of images and LUS score
- EIT data including quality and number of images, belt size used and regional ventilation measures (centre of ventilation, %Tidal volume per region and inhomogeneity index)

6.2.7 36-weeks' PMA BPD Assessment

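### The first-week FiO2 and ventilator-setting variables named in Section 6.2.3 are maxima since birth, so they can register worsening but not improvement by 72 hours or Day 7

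*Protocol*

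**What the plan says.** Protocol Section 6.2.3, in the list for the first week of NICU care, defines the oxygen variable as "Use of supplemental oxygen, including highest level of FiO₂ in the first 24, 48, 72 hours and 7 days of life". It defines the support settings as "Highest pressure, flow, delivered volume settings as appropriate for all types of respiratory support used during the first 24, 48, 72 hours" and 7 days. No lowest value, value per interval, or value in use at 72 hours or Day 7 is named for FiO2, pressure, flow or volume.

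The same list also collects "Details of respiratory support including type of support and duration (including none, low flow and high flow nasal cannula" and further modes), and intubation and extubation events up to Day 7. Section 6.2.8 adds the age at, and duration of, supplementary oxygen and each class of support from birth. Sections 6.2.4 and 6.2.5 place LUS, EIT and plasma at 72 hours and Day 7, each within 12 hours either way.

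For later visits, Section 6.2.6 fixes a clock time: "Type of respiratory support and use of supplemental oxygen at midday on Day 14 and Day 28". The delivery-room list in Section 6.2.3 takes both lowest and highest FiO2, and separately asks for the "Highest modified oxygenation index", given as SpO2/FiO2 and calculated afterwards.

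The Synopsis makes the primary outcome a set of endotypes from clinical, protein and imaging measures, by cross-sectional and longitudinal latent class analysis. Table 3a adds group-based trajectory modelling. Section 11.2 plans to code repeated predictors so that they capture change over time.

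**The concern.** A variable meant to describe change over the first week should be able to move in both directions. A maximum over windows that all start at birth cannot. On these fields a longitudinal class or trajectory can only be flat or rising, and that shape comes from the definition, not from the infants.

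Three uses are exposed:

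- **Day 7 phenotype.** Its level-of-support inputs may describe the first hours of life.
- **Ventilator settings and the plasma proteome.** Table 3a lists this among the intervention analyses. It would pair a current sample with a setting that may be days old.
- **Response to respiratory care.** This is an exploratory interest in Section 3.1.3. It would be seen through fields that cannot record a fall.

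The delivery-room SpO2/FiO2 item raises a smaller, separate question of direction.

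**Working it through.** No sample-size or power figure is involved, so there is no stated figure to reproduce. FiO2 values below are assumptions chosen to show the mechanism.

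**1. Nested windows.** Let M(t) be the highest value from birth to t. For t1 < t2, M(t2) = max{M(t1), peak between t1 and t2} ≥ M(t1). The field cannot decrease.

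**2. Three assumed infants.** Interval peaks are for 0–24 h, 24–48 h, 48–72 h and 72 h–Day 7.

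| Infant | Interval peaks | Recorded maximum since birth |
|---|---|---|
| A, weaned | 0.60, 0.40, 0.30, 0.21 | 0.60, 0.60, 0.60, 0.60 |
| B, persistent | 0.60, 0.60, 0.55, 0.60 | 0.60, 0.60, 0.60, 0.60 |
| C, worsening | 0.30, 0.40, 0.50, 0.60 | 0.30, 0.40, 0.50, 0.60 |

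C's change is visible. A's improvement is not, and A and B are identical on this field.

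**3. Age of the recorded value.** For a peak in the first 24 h:

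- At 72 h it is at least 72 − 24 = 48 h (2 days) old. At the early edge of the window, 60 − 24 = 36 h.
- At Day 7 (168 h) it is at least 168 − 24 = 144 h (6 days) old. At the early edge, 156 − 24 = 132 h (5.5 days).

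**4. Information lost in the field itself.** Illustrative simulation of 20,000 infants, half recovered. Early peak: mean 0.45, SD 0.10. Day 7 FiO2: centred on 0.22 if recovered, otherwise on the early peak minus 0.03. Noise is added and values are limited to 0.21–1.00. The AUC is for not recovered versus recovered:

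| Noise SD | Value in use at Day 7 | Maximum since birth |
|---|---|---|
| 0.03 | 0.970 | 0.509 |
| 0.06 | 0.939 | 0.532 |
| 0.10 | 0.875 | 0.562 |

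This compares two codings of one variable. It does not measure how well the full set of study data would perform.

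**5. What the other fields recover.** By Day 7 infant A is in air, so the oxygen-duration item in Section 6.2.8 separates A from B. In the 48–72 h interval both are still in oxygen (0.30 against 0.55). If both are on the same type of support, then type, extubation events and oxygen use agree, and the recorded FiO2 is 0.60 for each. No named clinical field then carries the difference in level.

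**6. SpO2/FiO2.** With assumed readings, 95/0.21 = 452 for a well infant and 80/1.0 = 80 for a sick one. The ratio rises as oxygenation improves, so the highest value marks the best moment.

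**The case against.** A reader might infer that the Day 7 phenotype cannot tell infants who recovered from those who did not. The Protocol does not support that. Support type (including none) and duration, extubation events, age at and duration of oxygen, LUS, EIT and plasma all bear on recovery, and the primary outcome uses the clinical, protein and imaging domains together. Settings are also recorded for each type of support used, so a step down in mode can show. This stands, and it limits the point to the level of oxygen and settings.

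A reader might also infer that no other first-week value is recorded. The documents do not establish that either. The list is introduced as data "relating to the clinical course during the first 24, 48, 72 hours and at 7 days of life, including", so it is not exhaustive and its stem has a separate phrase for Day 7. Table 5a schedules collection at each time point. The adverse-event definition in Table 7a needs a baseline FiO2 around every scan. Section 8.2.3 refers the full variable list to a Data Management Plan that is not shown. Completion per interval may be intended, but the two item definitions do not say so, and they are the only first-week FiO2 and settings variables the Protocol defines.

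Section 6.2.6 is not a precedent for recording levels. It fixes a midday time for support type and oxygen use only, not for FiO2 level, pressure or SpO2.

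Peak support is a legitimate severity measure, and Section 11.2 leaves variable selection open. Both are true. Neither lets the analyst recover a lower later value that was never entered.

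On SpO2/FiO2, the Protocol does not say the ratio will be formed from unpaired extremes. It leaves the pairing unstated.

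**Conclusion.** The point holds for the named variables. As written, first-week FiO2, pressure, flow and volume are cumulative maxima. They can show worsening but not a fall in level by 72 hours or Day 7, and they may predate the plasma and imaging they accompany by days. They are weak inputs for the planned longitudinal and trajectory analyses. The remaining data still carry some information on recovery.

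Any infant whose peak falls in the first 24 hours has the same value at all four time points. The Protocol does not give that share, so the effect on the endotypes or the BPD model cannot be sized. The conclusion rests on the plain reading that each window starts at birth, and on the Data Management Plan not already defining interval or current values. If it does, a sentence in Section 6.2.3 settles the matter.

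The SpO2/FiO2 point is minor and conditional: it applies if the item is meant to capture worst oxygenation.

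**What to change.** In Section 6.2.3:

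1. Define the highest FiO2, pressure, flow and volume over non-overlapping intervals: 0–24 h, 24–48 h, 48–72 h and 72 h–Day 7. The maximum since birth remains derivable as the largest interval value so far. The reverse derivation is impossible when a later peak is lower.
2. Record the FiO2, support type, settings and SpO2 in use at the 72-hour and Day 7 assessments, so that clinical level, imaging and plasma refer to the same moment.
3. If the delivery-room SpO2/FiO2 item is meant to show worst oxygenation, change highest to lowest, and state that it is calculated from simultaneous SpO2 and FiO2 readings.

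The cost is protocol and CRF wording and a few more fields from the same chart review, with no added procedure on the infant. It is cheaper early, since a late change means returning to the charts of up to 550 infants. This changes data definitions only; no clinical rule is proposed.
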